Sponsor	The sponsor is the party that commissions the organization or performance of the research, for example a pharmaceutical company, academic hospital, scientific organization or investigator (Sponsor-Investigator). A party that provides funding for a study but does not commission it is not regarded as the sponsor, but referred to as a subsidizing party.
RNA	Ribonucleic acid
PBMC	Peripheral blood mononuclear cell
SUSAR	Suspected Unexpected Serious Adverse Reaction
TAMU	Texas A&M University
UP	Unanticipated Problem
WHO	World Health Organization

SUMMARY

Rationale: SARS-CoV-2 spreads rapidly throughout the world. A large epidemic would seriously challenge the available hospital capacity, and this would be augmented by infection of healthcare workers (HCW). Strategies to prevent infection and disease severity of HCW are, therefore, desperately needed to safeguard continuous patient care. Bacille Calmette-Guérin (BCG) is a vaccine against tuberculosis, with protective non-specific effects against other respiratory tract infections in *in vitro* and *in vivo* studies, and reported morbidity and mortality reductions as high as 70%.^[1] Furthermore, in our preliminary analysis, areas with existing BCG vaccination programs appear to have lower incidence and mortality from COVID19^[2]. We hypothesize that BCG vaccination can reduce SARS infection and disease severity during the epidemic phase of SARS-CoV-2.

Objective: *Primary objective:* To measure the efficacy of BCG vaccination in high risk individuals (HRI) for infection with SARS-CoV2.

Secondary objective: To measure the efficacy of BCG vaccination among HRI in mitigating the severity of COVID19.

Study design: A placebo-controlled adaptive multi-center randomized controlled trial.

Study population: High risk individuals (HRI) including those with comorbidities (hypertension, diabetes, obesity, reactive airway disease, smokers), racial and ethnic minorities, elderly, teachers, police, restaurant wait-staff, delivery personnel; Health Care Workers; Health Care Workers (HCW) defined as personnel working in a healthcare setting, at a hospital, medical center or clinic (veterinary, dental, ophthalmology); and first responders (paramedics, firefighters, or law enforcement).

Intervention: Participants will be randomized between intradermal administration of BCG vaccine or placebo in a 1:1 ratio.

Study endpoints: *Primary endpoint:* incidence of SARS-CoV2 infection following BCG vaccination compared to placebo. *Secondary endpoint:* COVID19-related disease severity following BCG vaccination compared to placebo.

Nature and extent of the burden and risks associated with participation, benefit and group relatedness: Based on previous experience and randomized controlled trials in adult and elderly individuals, the risks of BCG vaccination are considered low. The objective of this trial is to evaluate the beneficial effects of BCG vaccination at a population level of high risk health care workers through a mitigated clinical course of SARS-CoV-2 infection. The primary endpoint and the adaptive design with interim analyses facilitate maximum efficiency of the trial, so that results can inform policy making during the ongoing epidemic.

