2. RESEARCH QUESTIONS

Primary Objective:

1. To measure the efficacy of BCG vaccination among HRI and HCW in preventing infection with SARS-CoV2 in the United States.

[figure not shown]
Secondary Objective:

1. To measure the efficacy of BCG vaccination among HRI and HCW in mitigating the severity of Covid-19 disease in the United States.

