10. SAMPLE SIZE AND STATISTICAL ANALYSIS

Data will be reported quantitatively. All analyses will be performed from the intention-to-treat principle. Missing data will be dealt with by multiple imputation using the mice package in R.

a. Sample size calculation

The study in the United States will include at least three sites: Houston (BCM and MD Anderson Cancer Center considered as 'one site' due to proximity), Texas A&M University (TAMU), and Cedars Sinai Medical Center (CSMC). TAMU will enroll 1400 individuals. The proposed enrollment sample size is designed to provide 80% power to detect a 60% vaccine efficacy (a relative risk of 0.4 among the vaccinated). This is based on the observed three-fold decline in respiratory infections in the South Africa adolescent cohort with 80% power and 0.05 type 1 error in a two-tailed test. We expect 5% of study participants to develop symptomatic COVID19 during follow-up, therefore a sample size of 1400, with 700 receiving intervention and 700 receiving placebo. We do not expect significant loss to follow up among HCWs (there has been zero LTF after the first 500 participants). We will plot Kaplan-Meier curves comparing COVID19 disease between the BCG and placebo groups and report hazard ratios and p-values using Cox proportional hazard models. DBS samples will be collected at baseline and weeks 4, 8, 12, 16, 20 and 24 post intervention. PBMCs and plasma donations are optional at baseline, 12 and 24 weeks. If interim analysis identifies a large proportion of participants to be seropositive before intervention, power analysis will be evaluated and an amendment will be submitted if additional participants need to be recruited.

b. Interim analysis

One month after the first 100 participants are enrolled, an interim analysis will be held by the independent statistician of the trial. Data will be exported independently from all sites and then data collated and merged for the interim analysis). The above described statistical analysis will be evaluated as well as safety profile. Enrollment is expected to occur within the first two months of launch. Interim analysis will occur based on study enrollment and three to six interim analysis will occur based on temporal dynamics of enrollment as requested by the DSMB. We will stop the clinical trial early if the p-value of any interim analysis is smaller than the pre-specified type-1 error cutoff. Each interim analyses will be reported to the DSMB.

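### The trial stops at the first significant interim look and reports the ordinary Cox hazard ratio; if the cutoff is 0.05 per look, a true 60% efficacy is reported with a median near 66%, and much less excess under a strict early boundary

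*Combined protocol and SAP*

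**What the plan says.** The Summary gives the purpose of the interims: "The primary endpoint and the adaptive design with interim analyses facilitate maximum efficiency of the trial, so that results can inform policy making". Section 2 makes estimation the primary aim: "To measure the efficacy of BCG vaccination among HRI and HCW in preventing infection with SARS-CoV2 in the United States". Section 10.a sizes the trial "with 80% power and 0.05 type 1 error in a two-tailed test" for a relative risk of 0.4, with 700 participants per arm, and states: "We expect 5% of study participants to develop symptomatic COVID19 during follow-up". It will also "report hazard ratios and p-values using Cox proportional hazard models", and 10.c repeats the Cox hazard ratio as the primary analysis.

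Section 10.b schedules the first interim one month after the 100th enrolment and three to six interims in all, as the DSMB requests. Its rule is: "We will stop the clinical trial early if the p-value of any interim analysis is smaller than the pre-specified type-1 error cutoff". The cutoff has no number there. The only type 1 error value in the section is the 0.05 in 10.a, and no boundary or alpha-spending function is named.

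No section describes an estimate or confidence interval that allows for stopping, or a minimum number of events before the trial may stop. Section 3.a makes follow-up depend on the interim results, up to 168 days.

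**The concern.** A trial that stops when its estimate is extreme enough, and then reports that estimate as if the analysis time had been fixed, tends to report an effect that is too large. Correcting the alpha level does not by itself cure this: a valid group-sequential boundary protects the p-value, while the ordinary estimate at the stopping time stays biased.

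It matters here because the early-stop result is the one the design is built to deliver. The Introduction wants a benefit identified as fast as possible. Section 10.k foresees applying a positive result quickly to the placebo group and to other hospitals. Section 7.d provides for offering BCG to placebo participants at the end of the study, subject to the DSMB. The estimate at an early stop could therefore be the last randomised one, with no full-follow-up figure to correct it.

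**Working it through.** **1. The plan's own figure.** Take p0 = 0.05 (10.a, read as the placebo rate) and p1 = 0.4 × 0.05 = 0.02, so the mean rate is 0.035.

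n per arm = [1.96·√(2 × 0.035 × 0.965) + 0.8416·√(0.05 × 0.95 + 0.02 × 0.98)]² / 0.03² = (0.5094 + 0.2180)² / 0.0009 ≈ 588, or 1176 in total.

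The stated 1400 is not reproduced from the stated inputs; 700 per arm gives 86.4% power for a single analysis. That is a separate matter. Expected events at full follow-up are 700 × 0.05 + 700 × 0.02 = 35 + 14 = 49.

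**2. Why the estimate is pulled upward.** With D events and equal arms, the standard error of the log hazard ratio is about 2/√D. At a per-look cutoff of 0.05, stopping for benefit needs an estimated efficacy of at least 1 − exp(−3.92/√D). With looks at about 18, 39, 60 and 81% of 49 events (assumed timing):

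| Events D | Smallest efficacy that stops the trial |
|---|---|
| 8.8 | 73% |
| 19.1 | 59% |
| 29.4 | 51% |
| 39.7 | 46% |
| 49 (final) | 43% |

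A trial stopping at the first of these looks must report at least about 73%, whatever the truth.

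**3. Simulation at true efficacy 60%.** Common inputs: 1400 participants 1:1, accrual over 60 days (10.b gives two months), 168 days of follow-up, constant hazards, no dropout.

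- Schedule A (assumed): interims at days 60, 95, 130 and 165 and a final at day 228; looks with fewer than 5 events skipped; stopping for benefit only; hazard ratio from events over person-time.
- Schedule B: first look 30 days after the 100th enrolment, the others evenly spaced by events, three or six interims, two-sided stopping, Cox estimate.

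| Per-look rule | A: median, all trials | A: median, early stops | B: mean, all trials | B: mean, early stops |
|---|---|---|---|---|
| p < 0.05 | 65 to 66% | 69 to 70% | 64 to 68% | 69 to 74% |
| Pocock | 64 to 65% | 71% | 63 to 65% | 72 to 74% |
| O'Brien-Fleming type | 62% | 67 to 68% | 61 to 62% | 69 to 70% |

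Under p < 0.05, 81 to 83% of trials stop early in A and 71 to 83% in B. The B median over all trials is 64 to 67%. The same B trials run to the end without stopping have a median of 60% (mean 58 to 59%).

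**4. Other true effects (5% placebo rate, p < 0.05 per look).**
- True 40%: all-trial mean 42 to 45%; early stops for benefit report 64 to 67% on average (B).
- True 25% (the lower figure in 10.f): all-trial mean 24 to 25% in B and median 26 to 27% in A, so 2 points of excess at most. In B, 17 to 29% of trials stop early for benefit and report 61 to 66% on average; in A the early-stop median is about 59%.

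**5. More events (assumed placebo rates, schedule A, true 60%).**
- 10% placebo rate, p < 0.05 per look: all-trial median 64 to 65%. With an O'Brien-Fleming-type boundary: 61%, and 62% after an early stop.
- 20% placebo rate, p < 0.05 per look: 61%.
- At true 40% the excess at these rates stays at about 4 to 5 points, so more events do not help equally at every effect size.

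**6. What adjustment achieves.** A median-unbiased estimate by stage-wise ordering (400 runs, true 60%) returned the all-trial median to about 58 to 60% and lowered the early-stop figure by about 3 to 5 points. From 69 to 70% that leaves roughly 64 to 67%.

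**The case against.** The strongest reply is that the size of the bias is not fixed by the documents, and this stands. A reader might infer that the published efficacy will be several points too high whatever happens. The plan does not support that, for three reasons:

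- The per-look cutoff is unstated, and an O'Brien-Fleming-type boundary cuts the all-trial excess to about 2 points.
- At true efficacy 25% there is almost no excess over all trials; the large errors there appear only among trials that stop early for benefit.
- The event count may be well above 49. The 5% in 10.a is symptomatic disease, whereas 10.c counts anyone PCR-positive or seroconverting. Section 10.a assigns the 1400 to one of at least three sites, and 10.b merges data from all of them.

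Two further points carry weight. The missing boundary is the prior defect, since no adjusted estimate can be computed without one. The shift is also modest beside the sampling error: with 35 and 14 events, 0.4 × exp(±1.96·√(1/35 + 1/14)) gives an efficacy interval of about 26 to 78%.

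It could also be argued that the paragraph on premature termination in Section 7 names only safety and futility for the interims. That does not rescue the plan, because 10.b sets an explicit p-value stop on the efficacy analysis. Look timing, constant hazards and uniform accrual are assumptions, but two quite different schedules agree.

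**Conclusion.** The point holds conditionally. The stopping rule, the unadjusted Cox estimate and the objective of measuring efficacy are all in the plan, and nothing links the estimate to the stopping rule.

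If the cutoff is 0.05 at each look, with 1400 participants, a 5% placebo rate and true efficacy 60%, the excess is about 6 points in the median over all trials and about 9 to 10 points after an early stop. Over all trials it falls to about 2 points with an O'Brien-Fleming-type boundary, about 1 to 5 points at an assumed 10 to 20% placebo rate, and about 2 points or less at true efficacy 25%. In that last case trials stopping early for benefit still report about 60%, close to the design value.

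It would go too far to say that an adjusted estimate must replace the Cox result as the sole primary figure. Statisticians could differ on that, and the adjustment removes only part of the early-stop excess. This is a cheap improvement in reporting that ranks below the missing boundary.

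**What to change.** First state the stopping boundary in 10.b. Then add to 10.b and 10.c that, after an early stop, efficacy will be reported as a median-unbiased hazard ratio with a stage-wise-ordering confidence interval matched to that boundary. Give the ordinary Cox hazard ratio beside it, labelled as unadjusted for stopping. Fix this before any efficacy look, so that the estimator is not chosen after the result is seen.

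The cost is a few lines of text and standard group-sequential software, with no added participants or data. The downside is a somewhat lower efficacy figure after an early stop and possibly a wider interval. The report should also say that the adjustment reduces the early-stop excess without eliminating it.

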1. INTRODUCTION AND RATIONALE

On 30 December 2019, a novel enveloped RNA betacoronavirus was detected from a patient with pneumonia of unknown etiology in Wuhan, the capital city of Hubei province. The pathogen was named the severe acute respiratory syndrome coronavirus-2 (SARS-CoV-2).^[3] Since beginning of 2020, SARS-CoV-2 spread rapidly throughout China and the rest of the world, the first detected case in the Netherlands on 27 February 2020. In the United States, there have been over 156,000 cases as of 30 March 2019.

From a cohort of patients with SARS-CoV-2 admitted to hospitals in the Wuhan region, (n=1099), a mortality rate of 1.4% was observed, with an ICU admission rate of 5% and 2.3% undergoing invasive mechanical ventilation.^[3]

The estimated basic reproduction number (R0) of SARS-CoV-2 is ~2.2-2.7 and, on average, each infected person spreads the infection to an additional two persons. SARS-CoV-2 is

being transmitted via droplets and fomites during close unprotected contact between an infector and infectee. According to WHO, as of 20 February 2020, 75,465 laboratory-confirmed SARS-CoV-2 cases were established. Health-care workers face an elevated risk of exposure to- and infection of- SARS-CoV-2, although in China, surprisingly, infection of health care workers could mostly be traced back to in-household transmission. Of these 75,465 laboratory-confirmed cases, 2,055 (2.7%) were reported among health care workers from 476 hospitals across China. The majority of cases (77.8%) were found in the working age (30–69 years).

In Wuhan, the hospital admission of SARS-CoV-2 infected patients substantially outweighed the number of physicians, leading to unsafe care and in-hospital transmission.[4] Consequently, in the district of Wuhan 40,000 health care workers have been deployed from other areas of China to support the response in Wuhan.

Subsequently, a SARS-CoV-2 pandemic reflects a serious threat to hospital personnel capacity, as the number of SARS-CoV-2 infected patients that require hospital care may well exceed the capacity of hospital personnel. It is imperative to ensure the safety, health and fitness of existing hospital personnel in order to safeguard continuous patient care. Strategies to improve the clinical course of SARS-CoV-2 infection are therefore desperately needed. To date, treatment for SARS-CoV-2 has been supportive, and no curative or protective treatments have been identified yet.

Bacillus Calmette-Guérin (BCG) was developed as a vaccine against tuberculosis, but many studies have shown its ability to induce potent protection against other infectious diseases: the so called non-specific effects (NSEs).[5] Moreover, BCG has non-specific clinical protective effects: early administration of BCG vaccination leads to reduced child mortality, mainly as a result of reduced neonatal sepsis, respiratory infections, and fever.[1, 5] NSEs of BCG are not limited to children, as a recent study in adolescents has shown a 70% decrease in the incidence of respiratory tract infections in individuals vaccinated with BCG compared to placebo.[6] In addition, a small Indonesian trial has shown that consecutive BCG vaccination for 3 months reduced the incidence of acute upper tract respiratory infections by 80% (95%CI=22-95%).[7] The non-specific beneficial effects of BCG are not restricted to infections, as BCG has also been used in patients with bladder cancer, to induce an improved reaction of the immune system, which prevents tumor progression and mortality.[8]

It has been recently demonstrated that the non-specific beneficial effects of BCG vaccination are due to epigenetic and metabolic reprogramming of innate immune cells such as myeloid cells and NK cells, leading to an increased antimicrobial activity, a process termed 'trained immunity'.¹² Upon stimulation with a pathogen, the innate immune system becomes primed and is able to react faster and more efficient to a secondary (and non-related) stimulus. In experimental studies, BCG has been shown to protect not only bacterial and fungal infections, but against viral infections such as influenza as well.[9] Furthermore, among humans receiving yellow fever vaccine virus, those who had received BCG had less viremia, and improved anti-viral responses compared to placebo treated subjects.[10] The observed effects are proposed to be due to modulation of the human innate immune system through 'trained immunity' and are long-lasting for at least one year

Based on the capacity of BCG to: i. reduce the incidence of respiratory tract infections in children and adults; ii. exert antiviral effects in experimental models; and iii. reduce viremia in an experimental human model of viral infection, we hypothesize that BCG vaccination may induce (partial) protection against susceptibility to and/or severity of SARS-CoV-2 infection. This study will evaluate the efficacy of BCG to prevent and improve the clinical course of SARS-CoV-2 infection.

BCG vaccine in immunocompetent adult people is considered safe, even in latently infected adults with prior infant BCG vaccination.[11] In a randomized controlled trial that compared revaccination with BCG versus placebo, no serious adverse events were observed in the BCG arm.[6]

Additionally, we have analyzed data and found that over the 15-day period from 9 March to 24 March 2020, the incidence of Covid-19 was 80 per million population, with a fatality of 0.55 per million. A total of 178 countries were in the database: current national programs of BCG vaccination exist in 131 countries; 21 countries have no current program of national BCG vaccination; and for 26 countries status is unknown. When we dichotomised the data according to those countries with and without BCG programs, the incidence of Covid-19 was 38.4 per million in countries with BCG vaccination whereas the incidence of Covid-19 was 358.4 per million in the absence of such a program. Likewise, the fatality recorded in countries with BCG programs was 4.28/million, compared to 40/million in countries without a national program. Calculating a crude case fatality rate (CFR) by dividing deaths by cases, countries with a BCG program the CFR was 0.13% and 0.33% in countries without a BCG program. Countries that have a booster injection of BCG 7 to 14 years later had no better outcomes than those with a single inoculation only. [2, 12].

A randomized controlled trial provides the highest validity for this research question. Given the immediate threat of the SARS-CoV-2 epidemic the trial has been designed as a pragmatic study with a highly feasible primary endpoint, that can be continuously (e.g. symptoms continuously and serology every other week) measured. This allows for the most rapid identification of a beneficial outcome that would allow other HRI and HCWs (including the control population) to also benefit from the intervention if and as soon as it has been demonstrated to be effective.

2. RESEARCH QUESTIONS

Primary Objective:

1. To measure the efficacy of BCG vaccination among HRI and HCW in preventing infection with SARS-CoV2 in the United States.

[figure not shown]
Secondary Objective:

1. To measure the efficacy of BCG vaccination among HRI and HCW in mitigating the severity of Covid-19 disease in the United States.

3. STUDY DESIGN

A placebo-controlled multi-center adaptive randomized controlled trial, see figure 2 for the logistics of the study.

Figure 2: Study design of the trial

a. Duration of Follow-Up

The duration of follow-up for each participant depends on the interim results of the primary endpoint and the probability of obtaining a result, with a maximum of 168 days. The end of the study is defined as the last patient's last registration in the mobile application. Study participants will collect fingerstick dried blood spot (DBS) samples for serology testing at baseline, weeks 4, 8, 12, 16, 20 and 24. If they develop symptoms, they will be qPCR tested by nasopharyngeal swab, oral swab and/ or fecal swabs.

[figure not shown]

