Participants will complete intermittent surveys via an electronic system every 7 days to assess the presence of any flu-like symptom, including sore throat, fever, headache, malaise, and cough. Note that this is part of routine surveillance for Covid-19 in health workers at the United States site. Consent forms will ask for consent to access this survey information.

Any positive response on the survey will trigger a nasopharyngeal, oral and/ or rectal swab to be collected to test for Covid-19 via rt-PCR

All participants, regardless of survey responses, will have serology for Covid-19 tested at 4 week intervals during the follow-up period (6 months)

If a participant completes the follow-up period and does not test positive for disease, their study participation is complete

If a participant does test positive for disease, their disease status will be ascertained for up to two months or until an outcome is available through one of the following mechanisms: (1) an electronic survey if they are not admitted to the hospital, including questions about the number of days they are ill, daily fever, and other symptoms; or (2) if they are admitted to the hospital, ordinal outcomes for disease severity will be extracted from the hospital's electronic medical records system.

During the first week of follow-up, all participants will actively be asked about any adverse events; thereafter, participants will report unsolicited AEs through the electronic survey. Vaccine related adverse events will be graded using the FDA guidance (<https://www.fda.gov/media/73679/download>) and noted using WHO-recommended Adverse event following Immunization forms (AEFI; <https://vaccine-safety-training.org/classification-of-aefis.html>).

Participants will have the option of donating 12 mL of blood for plasma (serology) and PBMCs for secondary analysis of immune correlates and for future analysis based on covid19-specific IgM and IgG. If they do not donate 12mL of blood, a fingerstick will be required for baseline COVID19 serology.

Dried Blood Spot (DBS): all participants will self-collect DBS samples at week 4, 8, 12, 16, 20 and 24. Envelopes to store the DBS are provided upon enrollment and can be mailed or dropped off at work and picked up by study coordinators.

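### Section 3.a lets interim efficacy results set the length of follow-up, so the final analysis could be timed from the data with no adjustment to the 0.05 test

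*Combined protocol and SAP*

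**What the plan says.** Section 3.a states that follow-up "depends on the interim results of the primary endpoint and the probability of obtaining a result, with a maximum of 168 days". It gives no threshold, no minimum follow-up, no decision-maker and no adjusted final test.

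Section 7.c describes a single schedule: all participants "will have serology for Covid-19 tested at 4 week intervals during the follow-up period (6 months"), with dried blood spots to week 24.

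Section 10.a sizes the trial for "80% power to detect a 60% vaccine efficacy (a relative risk of 0.4 among the vaccinated"), with "0.05 type 1 error in a two-tailed test". It adds "We expect 5% of study participants to develop symptomatic COVID19 during follow-up" and arrives at "a sample size of 1400, with 700 receiving intervention and 700 receiving placebo".

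Section 10.b plans three to six interim analyses at times that are not fixed. They are run by the independent statistician and reported to the DSMB. The trial stops if any interim p-value falls below a cutoff that is called pre-specified but is given no value. Section 9.c gives the DSMB's independent statistician access to unblinded data. Section 7, under premature termination, adds that safety and futility are reviewed at the interims, without a rule. No spending function, combination test, conditional-error method or fixed information target appears anywhere.

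**The concern.** Section 3.a names two things that can shorten follow-up: the interim primary results, and the chance of reaching a result. The second reads like conditional power. Section 10.b acts only on a p-value, so it does not account for that second driver.

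If follow-up can be closed because the unblinded comparison looks favourable, the final test is made at a moment selected for a high test statistic. Its p-value then no longer has its nominal meaning, even if only one significance test is ever done. A numerical boundary added to section 10.b, with section 3.a left alone, would leave this route open. The summary says that the results should inform policy during the epidemic, so the error rate of the primary test matters.

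The 5% incidence in section 10.a is a cumulative figure over follow-up. It has no fixed meaning unless the follow-up period is set.

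**Working it through.** **1. The plan's own sample size.** Inputs from section 10.a: two-sided 0.05, 80% power, relative risk 0.4, 5% incidence (read as the placebo rate, so 5% v 2%), and 700 per arm. No dropout is allowed for ("We do not expect significant loss to follow up among HCWs").

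n per arm = [1.96·√(2·0.035·0.965) + 0.8416·√(0.05·0.95 + 0.02·0.98)]² / 0.03² = (0.5094 + 0.2180)² / 0.0009 ≈ 588, or 653 with continuity correction.

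Power at 700 per arm = Φ[(0.03·√700 − 0.5094) / 0.2590] = Φ(1.098) = 86.4%.

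So 1400 is not reproduced exactly but is conservative. That mismatch is separate from this point. What matters here is that 5% is accrued over an assumed follow-up period.

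**2. The schedules side by side.** 24 weeks × 7 = 168 days. The maximum in section 3.a and the six months with week-24 sampling in section 7.c are therefore the same full schedule. The difference is that section 7.c states it flatly, while section 3.a makes it a ceiling that interim results can lower.

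**3. One interim, one final test at 0.05.** Assumptions not in the protocol: the score process behaves as Brownian motion, information grows with follow-up, and the interim falls at information fraction t₁. After the interim, the end date T (t₁ ≤ T ≤ 1) is chosen from the observed Z. The test rejects if |Z(T)| > 1.96. Type 1 error under no effect:

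| Rule | Type 1 error |
|---|---|
| Worst case, free choice of T, t₁ = 0.2 / 0.25 / 0.33 / 0.5 / 0.67 / 0.75 | 10.1 / 9.9 / 9.5 / 8.7 / 7.9 / 7.4% |
| Worst case, at least 10% more information required | 5.8-7.3% |
| End early if promising (\|Z\| above 1 to 1.96) | 5.6-7.7% |
| Choose the time with higher current-trend conditional power | 5.0-5.5% |
| End early if unpromising (\|Z\| below 0.5) | 4.0-4.8% |

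**4. Illustrative conditional-power rules.** Follow-up ends for everyone when Φ[(|Z|/√t − 1.96)/√(1−t)] reaches 0.8 or 0.9, and otherwise runs to day 168. One test is made at 1.96, with 1,000,000 simulated trials per rule and equally spaced decisions.

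- One decision, at half information: 7.8-8.0%.
- Three decisions: 9.4-9.8%.
- Six decisions: 9.4-10.4%.
- If conditional power below 0.1 also ends follow-up, across one to six decisions: 7.2-8.4%.

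**5. Does alpha spending cure it?** One interim at t₁ from 0.25 to 0.67, with two spending functions: O'Brien-Fleming-type, α(t) = 4[1 − Φ(z₁₋α/₄/√t)], and Pocock-type, α(t) = α·ln[1 + (e−1)t].

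- Maximum information fixed, and an early end at T spends only α(T): worst case 5.0% for both.
- All remaining alpha spent at a T chosen from interim results: worst case 6.8-8.6% (O'Brien-Fleming-type) and 5.7-7.5% (Pocock-type).

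At t₁ = 0.5 with O'Brien-Fleming-type spending, for example, the interim uses 0.0031. Spending the other 0.0469 at a freely chosen end date gives 7.7%.

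**The case against.** The strongest reply is that section 3.a adds no mechanism. The only ways the protocol describes for interim results to shorten the trial are the p-value stop in section 10.b and premature termination in section 7. Read with these, section 3.a says only that follow-up is shorter if the trial stops early. That reading is possible and may be what was meant. It does not explain the second driver in the sentence, and a text open to both readings does not protect the 0.05 level.

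A second reply is that the illustrative rules overlap with ordinary repeated testing. This is partly right. At half information, conditional power of 0.9 requires |Z| ≥ √0.5·(1.96 + 1.2816·√0.5) = 2.03, so every trial ended there is already significant. The one-decision result of 7.8-8.0% is indeed close to the 8.3% from two unadjusted tests. Much of the inflation would be removed by a proper boundary in section 10.b. The part that remains is an end date chosen from interim results and then tested with all the alpha left.

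A reader might also infer that the stated 80% power is lost. Under the three-decision rule, power at 5% v 2% does fall to 64-73%. But that happens because the assumed rule closes trials at one-quarter information with |Z| of only about 1.34 or 1.53; 27% or 17% of trials end early without significance. With one decision power is 83-88%. The protocol states no such rule, so the power claim is not supported.

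Nor do sections 3.a and 7.c flatly contradict each other: 168 days and week 24 are the same full schedule.

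**Conclusion.** The concern holds in a limited form. Section 3.a permits the final analysis to be timed from interim efficacy results, by a route that section 10.b does not cover and with no adjustment.

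The size is conditional on the rule: about 4-8% for rules with one interim decision, a worst case of about 7-10% with a free choice of end date, and about 9-10% for illustrative conditional-power rules with 3 to 6 decisions. These figures rest on assumed thresholds, spacing and information growth. A reader might take 7-10% as the trial's type 1 error, but the documents give no rule that would fix any single value.

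A reader might likewise conclude that alpha spending cannot help. That is true only if all remaining alpha is spent at an end date picked from interim results. With maximum information fixed and only accrued alpha spent, the error is 5.0%.

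**What to change.** Replace the first sentence of section 3.a with:

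> Every participant is followed for 168 days unless the trial is terminated on the DSMB's recommendation under the pre-specified interim boundary in section 10.b; otherwise the final analysis is done once, when the last participant reaches day 168.

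This removes the dependence on interim results and on the chance of reaching a result. State that conditional power may inform only a non-binding futility recommendation, never the length of follow-up or the date of the final test. Align sections 3.a, 7.c and 10.a on the same follow-up period, and say in section 10.a that the 5% incidence refers to it.

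Make the change together with a numerical alpha-spending boundary in section 10.b, with the maximum information fixed in advance. Either change alone leaves a gap.

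The cost is a few sentences of amendment. No extra participants are needed, and no visits beyond the week-24 sampling already scheduled. The sponsor gives up closing follow-up early on a promising trend that has not crossed the boundary.
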